#### **Day 1 (Visit 1)**

- Record medical history
- Assessment of LRTI-VAS
- Quality of Life-Bronchiectasis (QOL-B) questionnaire
- Leicester cough score
- Physical examination (including sputum characteristics, cough, dyspnoea, pleuritic chest pain, chills or rigors, and lung sounds) and vital signs (respiratory rate, heart rate, blood pressure, body temperature and oxygen saturation)

- Collection of demographic information, concurrent disease, concomitant medication use, and previous course(s) of antibiotic therapy in the preceding year
- Spirometry according to the standard criteria of the European Respiratory Society
- Concomitant medication monitoring
- Study drug and Innospire deluxe dispensation
- Inhalation tolerance test with either TIS or placebo (depending on randomisation) and first dose of study drug administered under supervision of study staff
- Instructions on proper administration and return of study drug and proper care of the nebulizer
- Diary card instruction

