#### **9.4.4 Secondary study parameter(s)**

Time to first exacerbation during the treatment period, as well as during the wash-out period, will be assessed using Cox proportional hazards regression and reported graphically using Kaplan-Meier estimates.

Statistical significance in change of FEV1 (percent of predicted) and FVC (percent of predicted) attributable to treatment will be calculated with a linear mixed-model analysis. The effect of time on outcome variables will be checked for linearity by means of plots and model Proportional hazards assumptions will be tested with log-minus-log plots. Time will be entered as an interval variable, with the number of intervals depending on the frequency of follow-up visits at which the outcome will be measured. Predefined confounders are entered stepwise as fixed effects. Predictors remain in the regression equation if the model fit increases significantly. Thereafter, random effects will be explored for intercept (patients) and slope (time and patients). If random effects do not change the model fit significantly, a fixed effect will be assumed. Change in quality of life was analyzed using linear mixed-model analysis as well. The minimal important difference (MID) in bronchiectasis was reported only for the Quality Of Life-Bronchiectasis questionnaire (QOL-B), with a minimal important difference (MID) for the Respiratory symptoms scale of 8 points represent clinical relevance. The MID for the leicester cough questionnaire in chronic cough is 1.3 points in total and represent clinical relevance. The Leicester cough questionnaire was initially developed for patients with chronic cough, but has been validated in patients with bronchiectasis. Consequently, the minimal important difference of 1.3 points will be used in this study and represent clinical relevance. Secondary to these questionnaires the LRTI-VAS questionnaire will be used. This questionnaire is a validated and reliable tool for symptom measurement in non-CF bronchiectasis.

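### Section 9.4.4 analyses change in FEV1, FVC and quality of life without specifying adjustment for the visit 1 value, which is collected and would sharpen mainly the patient-reported comparisons

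*Combined protocol and SAP*

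**What the plan says.** Section 9.4.4 states for lung function: "Statistical significance in change of FEV1 (percent of predicted) and FVC (percent of predicted) attributable to treatment will be calculated". The method it names is a linear mixed model. For quality of life it states: "Change in quality of life was analyzed using linear mixed-model analysis as well".

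On covariates, it says "Predefined confounders are entered stepwise as fixed effects" and "Predictors remain in the regression equation if the model fit increases significantly". The confounders are not listed there. The only covariate list in the plan is in 9.4.3, for the primary Poisson model. It holds treatment, age, sex, smoking history, *P. aeruginosa* and azithromycin use, and no baseline value of a secondary outcome.

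On structure, the number of time intervals follows from how often each outcome is measured at follow-up. For the random intercept and slope it says "If random effects do not change the model fit significantly, a fixed effect will be assumed". It does not say whether the dependent variable is a difference or the value at each visit, whether visit 1 is an outcome time point or a covariate, or whether the arms share a mean at visit 1.

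The schedule in 7.3 lists the "Quality of Life-Bronchiectasis (QOL-B) questionnaire" at visit 1, along with spirometry, the Leicester score and LRTI-VAS. All four are repeated at weeks 26, 52 and 56. Week 56 follows the four-week wash-out, and 9.4.4 does not say whether it enters the treatment contrast for these outcomes. No model is clearly named for LRTI-VAS.

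**The concern.** The visit 1 value of an outcome is usually its strongest single predictor, and here it is collected anyway. A change score fixes the coefficient of that value at 1. The best linear coefficient is rho when the variances are equal at both visits, so for rho below 1 the change score subtracts too much. The result is a wider interval than necessary. There is also an error, conditional on the observed baseline, that runs against the arm that happened to start higher.

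Using a mixed model does not settle this by itself. With visit 1 as an outcome row and a separate mean for each arm at that visit, the treatment-by-visit contrast is as imprecise as the change score.

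The trial has 29 patients per arm, and sections 7.2 and 9.2 mention no stratification. Sections 9.4.2 and 9.4.5 plan baseline comparisons of demographic variables. Nothing stated handles imbalance in these outcomes. Adjusted and unadjusted models both fit the text, so the choice could be made after the data are seen.

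**Working it through.** **Plan's own figure.** The documents give no sample size, SD, correlation or power for these outcomes, so there is none to reproduce. The only sample-size figure, 36 evaluable patients in 9.1, is for exacerbations. It does reproduce: (1.96·√4 + 0.8416·√6)² / (2.1·(ln 0.5)²) = 35.46, rounded up to 36.

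**Inputs.** 29 per arm (section 3); 18 evaluable per arm (9.1); QOL-B Respiratory MID of 8 points (9.4.4). Assumed: rho from 0.5 to 0.95, and a QOL-B SD of 15 to 25.

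**One follow-up visit, unit variance.**
- Change score: variance per patient 2(1 − rho).
- Adjusted for visit 1: 1 − rho².
- Ratio adjusted/change: (1 + rho)/2.
- The standard error (SE) of the arm difference is √(2/29) times the per-patient SD.

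| rho | SE, change | SE, adjusted | Variance ratio | SE cut | Per-arm n for change to match 29 adjusted |
|---|---|---|---|---|---|
| 0.5 | 0.263 | 0.227 | 0.75 | 13.4% | 38.7 |
| 0.7 | 0.203 | 0.188 | 0.85 | 7.8% | 34.1 |
| 0.9 | 0.117 | 0.114 | 0.95 | 2.5% | 30.5 |
| 0.95 | 0.083 | 0.082 | 0.975 | 1.3% | 29.7 |

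**Mean of weeks 26 and 52, equal correlations.**
- Change: (1 + rho)/2 + 1 − 2·rho = 1.5(1 − rho).
- Adjusted: (1 + rho)/2 − rho² = (1 − rho)(1 + 2·rho)/2.
- The ratio is (1 + 2·rho)/3: 0.67, 0.80 and 0.93 at rho = 0.5, 0.7 and 0.9.

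**Mixed-model forms.** A simulation of 20,000 trials (three visits, equal correlations, known variances, 29 per arm) compared three analyses. A mixed model with free arm means at visit 1 gave the same SE as the change score: 0.262, 0.206 and 0.118 SD at rho = 0.5, 0.7 and 0.9. With a common baseline mean, the SEs were 0.225, 0.189 and 0.115.

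**Chance imbalance.** The SE of the baseline difference is √(2/29) = 0.263 SD, so P(|difference| ≥ 0.3 SD) = 2(1 − Φ(0.3/0.263)) = 25%. At 18 per arm the SE is 0.333 SD and the probability about 37%. A change score carries −(1 − rho) of the difference: a 0.3 SD difference shifts the effect by 0.15 SD at rho = 0.5 and 0.03 SD at 0.9. With an SD of 20 that is 3 points and 0.6 points, against the MID of 8. Simulated slopes were −0.51, −0.30 and −0.10 at rho = 0.5, 0.7 and 0.9. With a common baseline mean they were close to zero.

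**Power for the 8-point MID, 29 per arm, change then adjusted.**

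| Assumed SD | rho = 0.5 | rho = 0.7 |
|---|---|---|
| 15 | 53% → 65% | 75% → 81% |
| 20 | 33% → 42% | 50% → 57% |
| 25 | 23% → 29% | 35% → 40% |

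**The case against.** The strongest reply is that 9.4.4 is silent, not expressly unadjusted. Change attributable to treatment, next to a time effect and random intercepts and slopes, can describe a longitudinal model of visit values. If that model gave both arms one mean at visit 1, it would already deliver the adjusted result. The unlisted confounders might also include the baseline value. This stands: a reader might infer that the plan rules out adjustment, and the text does not say so. It does not remove the point, because a baseline term among the confounders would still face the significance-based retention rule, and nothing in the plan requires a common baseline mean.

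A reader might also infer that baseline imbalance stays in the effect and biases it. It does not. A change score removes the whole difference and over-corrects by (1 − rho). Under randomisation the estimate is unbiased, and its SE already reflects this variation. The loss is in precision and in the error conditional on the observed imbalance.

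The size depends on inputs that the documents do not give. Three points of QOL-B error combines the lowest assumed rho, an imbalance reached in about one trial in four, and an assumed SD of 20. If rho is 0.9 to 0.95, as may hold for FEV1 and FVC, the SE gain is only about 1% to 3%.

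Finally, it is tempting to say that LRTI-VAS falls back on the t or Mann-Whitney tests of 9.4.1. That is an inference: LRTI-VAS appears in the same paragraph as the mixed model for quality of life. What can be said is that its model is not clearly named.

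**Conclusion.** The point holds as a gap in specification with a real but modest cost. Section 9.4.4 does not secure adjustment for a visit 1 value that the trial collects for all five outcomes. Under a subtracted score, or a mixed model with free arm means at visit 1, the SE is larger than it need be. Adjustment would cut it by about 13% at rho = 0.5, 8% at 0.7, 2.5% at 0.9 and 1% at 0.95. These figures assume one follow-up visit and equal variances, with rho assumed throughout. The benefit is mainly for QOL-B, the Leicester score and LRTI-VAS if their rho is moderate, and small for FEV1 and FVC if theirs is high.

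The documents do not support the wider statement that every secondary interval is bound to be too wide, because that depends on which model is fitted. These are secondary outcomes with no stated power, and the primary Poisson analysis in 9.4.3 is untouched. The change is still worth making before the analysis, since it is nearly free and removes an analyst's choice.

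**What to change.** In 9.4.4, for FEV1, FVC, QOL-B, Leicester score and LRTI-VAS, state that:

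- the dependent variable is the value at each post-baseline visit;
- the visit 1 value of the same outcome is a fixed covariate, forced in and exempt from stepwise removal;
- the treatment contrast uses weeks 26 and 52, and the week 56 wash-out visit is reported separately.

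Alternatively, specify a longitudinal model with visit 1 as an outcome row and a common baseline mean for the two arms. The two options are not interchangeable when visit 1 values are missing. The covariate version drops those patients unless the value is imputed; the common-baseline model keeps them.

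The cost is one or two sentences and about one degree of freedom per model. No new data are needed.

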## **7.3 Study procedures**

Patients with bronchiectasis and who fulfil the inclusion and exclusion criteria will be asked to participate in the study. After a run-in period of 4 weeks' patients will be randomized to receive one of the two possible treatment regimens: TIS OD 300 mg daily or placebo. Administration will be continuous for the full 12 months. According to the parallel group design patients will be treated for 52 weeks. After completing the intervention period patients will have a follow-up (wash out period) of 4 weeks. This wash-out period was considered to be one month, in which time the antimicrobial effect of the antibiotic supposedly disappears, as suggested in earlier studies.

Subjects will be evaluated at run-in = visit 0 (week -4), visit 1 (day 1- start of the study), visit 2 (week 13), visit 3 (week 26), visit 4 (week 39), visit 5 (week 52: end of treatment) and visit 6 (run-out; week 56: end of the study). One week after start of treatment a phone call will be scheduled. Clinical, laboratory, and bacteriology evaluations will be determined according to the schedule (Figure 1: study schedule). Subjects who terminate treatment should be followed for the same period as those who complete the study, according to the study schedule.

During the study any changes in medical condition and compliance with medication will be filed in the diary card.

At visit 1, after randomisation, a tolerance test with either TIS or placebo (blinded according to randomisation) will be performed. Before nebulizing TIS patients are treated with salbutamol 200mcg using an AeroChamber. During tidal breathing patients inhale 300mg TIS or placebo (at room temperature) by using the Innospire Deluxe nebulizer with mouthpiece during approximately 5 minutes. If patients develop a moderate-severe bronchial obstruction, patients are excluded from the study. The severity of bronchial obstruction and coughing is assessed by a specialized nurse, the respiratory physician or the own GP. An exacerbation is defined as the presence of three or more of the following symptoms or signs for at least 24 hours: increased cough, increased sputum volume, increased sputum purulence, haemoptysis, increased dyspnoea, increased wheezing, fever (>38.5°C)

or malaise, and the treating physician agreed that antibiotic and/or prednisolone therapy was required.

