**Week 56 (run out, Visit 6)**

- Record medical history (exacerbation, antibiotics?)
- Assessment of LRTI-VAS
- Quality of Life-Bronchiectasis (QOL-B) questionnaire
- Leicester cough score
- Diary card check
- Repeat laboratory examination (CRP, Hb, WBC, Sodium, Potassium, Creatinin, eGFR, Liver Function)
- Sputum examination for microbiologic assessment
- Spirometry according to the standard criteria of the European Respiratory Society

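### The mixed models for FEV1, FVC and quality of life neither exclude the off-treatment week-56 visit nor name a contrast, so the treatment effect may be diluted by an amount that depends on an open choice

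*Combined protocol and SAP*

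**What the plan says.** Section 9.4.4 states that the change in FEV1 and FVC "attributable to treatment will be calculated with a linear mixed-model analysis", and that "Change in quality of life was analyzed using linear mixed-model analysis as well". Time goes in as an interval variable, "with the number of intervals depending on the frequency of follow-up visits at which the outcome will be measured". The section adds that "The effect of time on outcome variables will be checked for linearity by means of plots", but does not say what follows if the plots show curvature. It names no visit, slope or average as the effect attributable to treatment.

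The visit lists in section 7.3 place spirometry, QOL-B, the Leicester score and LRTI-VAS at day 1, week 26, week 52 and week 56. Weeks 13 and 39 have none of them. The week-56 list includes "Spirometry according to the standard criteria of the European Respiratory Society". The same section gives the last two visits as "visit 5 (week 52: end of treatment) and visit 6 (run-out; week 56: end of the study" and uses the word follow-up for the four wash-out weeks between them. It justifies their length as a time "in which time the antimicrobial effect of the antibiotic supposedly disappears".

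For time to first exacerbation, section 9.4.4 does distinguish the treatment period from the wash-out period. It makes no such distinction for the mixed models.

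**The concern.** Week 56 is a follow-up visit at which these outcomes are measured, so the literal rule admits it. A difference that builds up on treatment and shrinks after the drug stops would then be fitted as one trend over 56 weeks, or averaged over on- and off-treatment visits. Either way the estimate moves toward zero.

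Section 9.4.4 reads these outcomes against minimal important differences: 8 points on the QOL-B Respiratory symptoms scale and 1.3 points on the Leicester total. A true difference of that size could be reported as falling well short of it.

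The same mechanism works against detecting harm. The table in section 6.3 lists four trials with a non-significant FEV1 decrease on active treatment, and section 3 names serial spirometry as a safety parameter. A fall in FEV1 on treatment that reversed off drug would be diluted in the same way.

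Because the contrast is not named, the choice among quite different estimates could be made after the data are seen.

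**Working it through.** The documents give no figure for these models, so there is none to reproduce.

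**Inputs.** Measurement times are t = 0, 26, 52 and 56 weeks (section 7.3). D is the true arm difference at week 52. Two shapes are assumed up to week 52: linear build-up, with differences 0, 0.5D, D; and full effect by week 26, with differences 0, D, D. The share of D remaining at week 56 is also an assumption, taken as none or half.

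**Common terms.** Mean t = (0 + 26 + 52 + 56)/4 = 33.5. The deviations are −33.5, −7.5, 18.5 and 22.5. Sxx = 1122.25 + 56.25 + 342.25 + 506.25 = 2027. With complete balanced data the random-intercept slope equals the least-squares slope.

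**Treatment-by-time slope × 52**, with Sxy = Σ(t − 33.5) × difference:
- Full loss, linear: Sxy = −3.75 + 18.5 = 14.75; 14.75 × 52/2027 = 0.38.
- Full loss, full effect by week 26: Sxy = −7.5 + 18.5 = 11; 11 × 52/2027 = 0.28.
- Half loss, linear: Sxy = 14.75 + 11.25 = 26; 26 × 52/2027 = 0.67.
- Half loss, full effect by week 26: Sxy = 11 + 11.25 = 22.25; 22.25 × 52/2027 = 0.57.

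**Fitted arm difference at week 52** (linear model with treatment and interaction), equal to mean difference + 18.5 × Sxy/2027:
- Full loss: 0.375 + 18.5 × 14.75/2027 = 0.51; 0.50 + 18.5 × 11/2027 = 0.60.
- Half loss: 0.50 + 18.5 × 26/2027 = 0.74; 0.625 + 18.5 × 22.25/2027 = 0.83.

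**Average of post-baseline visits**, relative to the average of weeks 26 and 52:
- Full loss: (0.5 + 1 + 0)/3 ÷ 0.75 = 0.67; (1 + 1 + 0)/3 ÷ 1 = 0.67.
- Half loss: 0.667/0.75 = 0.89; 0.833/1 = 0.83.

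| Reading of the treatment effect | Full loss | Half loss |
|---|---|---|
| Slope × 52, share of D | 0.28–0.38 | 0.57–0.67 |
| Fitted week-52 difference, share of D | 0.51–0.60 | 0.74–0.83 |
| Post-baseline average, share of its on-treatment value | 0.67 | 0.83–0.89 |
| Categorical week-52 contrast, share of D | 1.00 | 1.00 |

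**Reference without week 56** (weeks 0, 26, 52). The slope × 52 is 1.00 for both shapes. The fitted week-52 difference is 1.00 for linear build-up and 1.17 for full effect by week 26, because a straight line overshoots a step.

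**Simulation check.** One simulated random-intercept mixed model with full effect by week 26 and full loss gave a slope × 52 of about 0.30 with week 56 and 1.03 without it.

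**On the plan's own thresholds, full loss.** A true 8 points on the Respiratory symptoms scale would read 2.3 to 3.0 from the slope or 4.1 to 4.8 from the fitted week-52 difference. A true 1.3 on the Leicester total would read 0.37 to 0.49 or 0.66 to 0.78.

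**The case against.** Section 9.4.4 never says that week 56 is in the model; that follows from general wording and the absence of an exclusion. A number of intervals fits discrete occasions as well as it fits a straight line in weeks, and if time is categorical a week-52 contrast is not diluted. The planned plots could show a rise followed by a reversal. These points stand. They rule out treating the inclusion of week 56, or a linear trend, as a declared rule. They do not settle the matter, because no contrast is named and nothing is prescribed if the plots look curved.

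A reader might infer that the plan shrinks the effect to about a third. That needs linear time in weeks, the slope taken as the effect, and complete loss by week 56, all together. Section 7.3 speaks only of the antimicrobial effect, with the qualifier supposedly. It says nothing of FEV1, cough or quality of life returning to baseline. Section 6.3 reports that sputum density returned to baseline off drug in cystic fibrosis, and section 12.1 links bacterial killing to symptoms, so some loss is plausible; its size is not documented. For FEV1, the trials in section 6.3 do not lead one to expect a benefit that could be lost.

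It is also fair that weeks 26 and 52 are not on-treatment visits for everyone. Sections 7.3 and 7.6 follow patients who stop treatment on the same schedule, section 7.5 expects 30% drop-out, and section 9.4.1 specifies intent-to-treat. A restriction to on-treatment data would be the wrong remedy.

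**Conclusion.** The point holds. Followed literally, the plan lets an off-treatment value into the effect attributed to treatment, and it leaves the contrast open. Under full loss by week 56, the four readings run from 0.28 to 1.0 of the relevant on-treatment value. Under half loss, the slope gives 0.57 to 0.67 and the fitted week-52 difference 0.74 to 0.83. These figures rest on the two assumed shapes, the assumed loss, and complete data without treatment discontinuation.

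The documents do not support the firmer statement that the effect will be cut to about a third. That is the low end of the range, under one reading and one assumption. The Poisson analysis of exacerbations is untouched, and the dilution pulls toward no difference, for benefit and for reversible harm. It should be corrected, but it does not threaten the primary result.

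**What to change.** In section 9.4.4, state that the treatment effect on FEV1, FVC and the questionnaires is estimated from the scheduled treatment-period visits (day 1, weeks 26 and 52) for all randomised patients, regardless of treatment discontinuation. Enter visit as a categorical factor and name the week-52 between-arm contrast as the reported effect. Analyse the change from week 52 to week 56 separately as the wash-out result.

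Assign early-termination assessments by their actual date. Sections 3 and 5.3 make the final-visit assessments the minimum record for patients withdrawn from study drug, so a value taken during the treatment period could otherwise carry the post-wash-out label. This needs a rule for matching dates to scheduled visits.

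The cost is a wording change plus that rule, with no new data. A categorical visit term uses slightly more degrees of freedom than a linear one, and week 56 no longer contributes to the main estimate, though it is still reported.

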### **9.4 Methods of analysis**

#### **9.4.1 General statistical considerations**

All data will be collected and analysed using SPSS statistics 20.

Statistical analysis will be performed on an intent-to-treat basis by the investigator and an independent statistician. All continuous variables will be tested for normal distribution with the Kolmogorov-Smirnov test for normal distribution. The Student-t test will be used for normally distributed variables, the Mann-Whitney U test for not normally distributed variables and the  $\chi^2$  test for dichotomous variables. The software package SPSS 20 for Windows (IBM-SPSS Inc., Chicago, Illinois, USA) is available for statistical analysis. A value of  $p < 0.05$  will be considered significant.

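### Section 9.4.4 lets significance tests on the outcome data choose the covariates and random effects of the mixed model; a treatment-by-time test built that way would be mildly too liberal

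*Combined protocol and SAP*

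**What the plan says.** Section 9.4.4 sets out a model-building sequence for lung function. The target is "Statistical significance in change of FEV1 (percent of predicted) and FVC (percent of predicted) attributable to treatment", estimated with a linear mixed model. On covariates: "Predefined confounders are entered stepwise as fixed effects", and "Predictors remain in the regression equation if the model fit increases significantly". Only after that step are a patient intercept and a patient slope over time examined, and "If random effects do not change the model fit significantly, a fixed effect will be assumed". Time is handled as follows: "Time will be entered as an interval variable, with the number of intervals depending on the frequency of follow-up visits". For quality of life the section adds: "Change in quality of life was analyzed using linear mixed-model analysis as well".

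The section names no test or threshold for these steps, beyond the general p < 0.05 of section 9.4.1. It gives no covariance structure, list of confounders or fallback, and it names no treatment-by-time term. By contrast, section 9.4.3 fixes the covariates of the primary Poisson model in advance.

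The visit lists in section 7.3 place spirometry and the questionnaires at day 1 and weeks 26, 52 and 56. Three of these four occasions fall within the treatment period. Sections 3 and 4.4 plan 58 randomised patients (29 per arm), with 18 evaluable per arm required.

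**The concern.** The lung-function and quality-of-life results come from a model whose form depends on the data being tested. A p-value taken from a model chosen this way need not hold its nominal level.

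The weak spot is the random slope. With few visits and a small trial, its test can easily miss real differences in patients' trends. The reduced model then treats those trends as independent noise, and the standard error of any effect that involves change over time is too small.

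The patient intercept is not the worry. In repeated spirometry the correlation within patients is normally so strong that its test would almost always keep it.

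Separately, a covariate set chosen by significance can differ between FEV1, FVC and quality of life, which makes their treatment effects harder to compare.

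**Working it through.** **1. The plan's own figure.** The documents give no figure for the mixed models. The only related number is the evaluable sample size in section 9.1, which reproduces. With a binary covariate at 0.5, rate 2.1, ratio 0.5 and phi 1, the variance terms are 1/0.5 + 1/0.5 = 4 under the null and 1/0.5 + 1/(0.5 × 0.5) = 6 under the alternative. So N = (1.960 × √4 + 0.8416 × √6)² / (2.1 × (ln 0.5)²) = 5.9815² / 1.009 = 35.46, rounded up to 36. The check therefore uses both 29 and 18 per arm.

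**2. Assumptions not in the documents.** Time is linear, data are complete, and the quantity tested is treatment-by-time. Let r be the SD of true one-year patient slopes divided by the residual SD. The intraclass correlation is 0.85 in steps 4, 5 and 7.

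**3. What happens if a real slope is left out.** With m visits and S the sum of squared deviations of visit times in years, the ratio of true to assumed variance under a random-intercept model is

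V = (1 + S r²) / (1 + S r²/(m − 1)).

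- Weeks 0/26/52: S = 0.50. At r = 1, V = 1.50/1.25 = 1.20, and the error is 2[1 − Φ(1.96/√1.20)] = 0.074.
- Weeks 0/26/52/56: S = 0.75. At r = 1, V = 1.75/1.25 = 1.40, and the error is 0.098.
- At r = 2, V = 1.5 and 2.0, and the errors are about 0.11 and 0.17. Simulation agrees (0.10–0.11 and 0.17–0.18).

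These are the errors if the slope were never fitted. That is not the plan's rule.

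**4. How often the rule drops the slope.** REML simulation under no treatment effect, 4,000 runs per scenario, with a 2-df likelihood-ratio test at 0.05:

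| Visits, n per arm | r=0.5 | 0.75 | 1 | 1.25 | 1.5 | 2 |
|---|---|---|---|---|---|---|
| 3 visits, 29 | 94% | 85% | 69% | 40% | 18% | 1% |
| 3 visits, 18 | 94% | 90% | 79% | 59% | 38% | 9% |
| 4 visits, 29 | 90% | 67% | 33% | 8% | 1% | 0% |
| 4 visits, 18 | 92% | 78% | 53% | 25% | 8% | 0.4% |

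**5. Type I error under the rule.** The treatment-by-time test is taken from whichever model the rule selects. The highest values are:

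- 3 visits, 29 per arm: 0.070 (r = 1)
- 3 visits, 18 per arm: 0.069 (r = 1.25)
- 4 visits, 29 per arm: 0.060 (r = 0.75–1)
- 4 visits, 18 per arm: 0.079 (r = 1)

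The error is back near 0.05 once r reaches 1.5–2. With the slope always kept it is 0.036–0.057 throughout. Monte Carlo error is about ±0.007. The 0.079 cell is probably a little high by chance, since the always-kept model gave 0.057 in the same simulated trials.

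**6. The same check on the FEV1 % predicted scale.** Patient SD 18 (assumed), REML with t-tests, 20,000 runs per case:

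| Design | Slope SD / residual SD | Slope retained | Error, plan's rule | Error, slope always kept |
|---|---|---|---|---|
| 4 visits, 29 per arm | 3/4, 3/3, 4/4 | 29–62% | 6.5–6.7% | 4.7–5.2% |
| 18 per arm | same | – | 6.9–7.2% | 4.5–4.9% |
| 3 visits, 29 per arm | same | 13–28% | 6.0–6.6% | – |
| 4 visits, 29 per arm | 4/3 | 93% | 5.0% | – |

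A smaller simulation (2,000 runs per case) across both sample sizes and both visit sets gave 5.8–7.3% under the rule and 4.2–5.5% with the slope always kept. Its 4/3 case with four visits and 29 per arm again showed 93% retention, with 5.8% error.

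**7. The covariate step.** Covariates are chosen before any random effect enters, so repeated visits count as independent. For a patient-level covariate the variance is understated by 1 + (m − 1) × 0.85, which is 2.70 for three visits and 3.55 for four. An irrelevant covariate then passes a 5% test with probability 2[1 − Φ(1.96/√2.70)] = 0.23 or 2[1 − Φ(1.96/√3.55)] = 0.30. In complete, balanced data, however, a time-constant main effect leaves the treatment-by-time estimate unchanged. This step therefore does not produce the excess in step 5.

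**The case against.** The strongest reply is that the two halves of the problem offset each other. Small slope variation is often dropped but costs little, while large variation would cost a lot but is nearly always kept. This stands. The two coincide only in a middle band, and every variance used here is assumed. Errors of 10–18% belong to a model that never fits slopes, so they should not be charged to this rule.

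Four stronger readings are tempting, and the documents do not support them:

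- **The plan specifies a treatment-by-time test that fails its level.** Section 9.4.4 speaks only of change attributable to treatment. Treatment-by-time is the natural reading but is not stated. If another contrast is meant, or if time is categorical, these figures do not carry over directly.
- **The excess is shown for quality of life.** Nothing in the documents gives its variance components. That the selection steps apply to it is inferred from its being analysed by mixed model as well.
- **Stepwise covariate selection causes the inflation.** Step 7 shows that it does not. The confounders are also called predefined, so selection is at least within a fixed list, although this section does not give that list.
- **The trial's main conclusion is at risk.** The primary Poisson model has its own fixed covariates and is untouched.

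None of this defends the rule. It remains a stated procedure that lets the outcome data choose the model, and a better alternative costs almost nothing.

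**Conclusion.** The point holds as a modest defect in the secondary analyses. With three or four occasions and 36 to 58 patients, the rule often discards a real random slope when slope variation is small to moderate. A treatment-by-time test would then run at about 6–7.5%, with about 8% the highest value simulated, instead of 5%. That is an excess of roughly 1 to 2.5 percentage points, and keeping the slope removes it. When slope variation is large relative to residual noise, the error under the rule returns to about 5–6%.

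These sizes rest on assumed variances, linear time, complete data and a treatment-by-time contrast. The selection rule itself, and the possibility that covariate sets differ between endpoints, can be read directly from section 9.4.4 and rest on no assumption. The change should be made, but nothing here threatens the primary result.

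**What to change.** In section 9.4.4, delete the stepwise entry and retention of confounders, and delete the sentence that falls back to a fixed effect. Replace them with one model for FEV1, FVC and quality of life that states:

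- one fixed covariate set, for example that of the primary model in section 9.4.3;
- one within-patient covariance, kept whatever its p-value: unstructured across visits, or random intercept plus slope;
- a simpler structure to be used only if the model fails to converge, named in advance;
- the treatment contrast to be tested, how time is coded, and whether the off-treatment week 56 value contributes to it.

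The cost is SAP wording only, with no new data or patients. The statistical price is slightly wider intervals if slopes truly do not vary. In that case (r = 0) the always-kept model was a little conservative, at 3.6–4.4% with 18 per arm and with four visits at 29 per arm.
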